2 BACKGROUND INFORMATION AND SCIENTIFIC RATIONALE

2.1 Background Information

The natural history of congenitally acquired CMV infection is well described.¹⁻⁷ In contrast, outcomes of perinatally and postnatally acquired CMV infections are less well characterized. It is generally agreed that postnatal acquisition of CMV in term infants does not lead to symptomatology or disease.⁸ In preterm infants, initial case reports suggested that peri- and postnatally acquired CMV infections could produce severe disease.⁹⁻¹⁴ Larger series and case-controlled trials more recently suggest that symptomatic disease in preterm babies is less common than asymptomatic infection, and long-term sequelae are rare.¹⁵⁻¹⁹ Nevertheless, severe disseminated CMV disease can occur in premature infants, including life-threatening pneumonitis, hepatitis, and thrombocytopenia.²⁰ Antiviral therapy in such patients is frequently used, albeit without either controlled data to demonstrate benefit or knowledge of proper dosing regimens.¹² In patients with symptomatic congenital CMV disease, six weeks of intravenous ganciclovir improves hearing outcomes in early childhood,²¹ and may benefit neurodevelopmental outcomes as well.²² In premature babies with visceral disease from postnatally acquired CMV, the goal of antiviral therapy is different; namely, it is to treat the end-organ disease, which is occurring at that time, rather than to prevent or improve long-term sequelae. Without efficacy data, the duration of treatment is variable, but anecdotal experience suggests that it generally is in the range of two to four weeks of total antiviral therapy. Approximately two-thirds of treated neonates receiving six weeks of intravenous ganciclovir develop Grade 3 or 4 neutropenia (utilizing the DAIDS Toxicity Tables) during therapy.²¹

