8.2.1.1. CMV Viral Load/Resistance Testing

[figure not shown]
Assessment of CMV viral load in whole blood will be conducted at the UAB Central Laboratory. The required amount of whole blood for CMV PCR is 0.5 mL. Whole blood will be collected at each study visit from Period 1 through Period 5. Whole blood will also be collected at the Period 6 study visit if the

subject weighs at least 600 grams, and at the Period 7 study visit if the subject weighs at least 650 grams.

Urine collection by noninvasive mechanism (e.g., bagged, indwelling foley catheter, excess clinical specimen, etc.) will be attempted at each study visit. If urine is obtainable, it will be frozen and sent to the UAB Central Laboratory for processing. If an attempt to obtain urine for CMV detection is unsuccessful, study staff will document the failed attempt on a source document. All specimens collected will be sent to the UAB Central Laboratory.

Viral detection assays will be performed in the UAB Central Laboratory. These assays and tests are in clinical and research use already in the Central Laboratory. The detection of CMV DNA will be performed using the CMV two primer Taqman assay already employed regularly in our laboratory. The detection limit of our real-time PCR assay, as determined by the sensitivity titration analysis, is 10 genomic equivalents per reaction. The results of 10 different runs on different days are shown in the Table below. Regression analysis shows a very high correlation coefficient (0.9996) for the 6 log concentration range (see Figure below).

genome equivalents	log(10)	# +/10	ct(mean)	std
1000000	6	10/10	18.362	0.085609
100000	5	10/10	21.476	0.155863
10000	4	10/10	24.855	0.187157
1000	3	10/10	28.321	0.305449
100	2	10/10	31.869	0.2283
10	1	10/10	35.283	0.606045

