11.2 Sample Size Considerations

The primary outcome used for power analysis is the area under the curve for 12 hours (AUC12) following 6 mg/kg of ganciclovir. In a one-way ANOVA design, we would like to compare the means of 4 groups (see below) with sample sizes of approximately 8, 8, 8, and 8 (32 total subjects enrolled across the four cohorts). If the means of the AUC12 of the 4 groups are 20, 20, 30, and 35 assuming a common standard deviation of 10, these mean differences (equivalent to an effect size of 0.72) will be detected at 83% power using an F test with 0.05 level of significance. In order to look at other possible scenarios, we provide the table below that looks at other standard deviation values, its corresponding effect size given the differences in means as described above, and the power of detecting such a difference/effect size. If estimating the AUC without regard to the groups, the margin of errors associated with a 95% confidence interval assuming different standard deviation values and a sample size of 32 are given in the table below.

Standard Deviation	S=8	S=9	S=10	S=11
Effect Size	0.81	0.72	0.64	0.59
Power	96%	91%	83%	75%
Margin of Error	2.33	2.62	2.91	3.20

The above parameter values were hypothesized based on results from other studies.^{25,34} It is worth noting that there are no PK data in this population and the results are likely to be different from other studies due to the maturational changes.

Following enrollment, subjects will be stratified by gestational age and by chronologic age as follows: 1) \leq 27 weeks 6 days gestational age at birth and \leq 30 days chronologic age at study enrollment; 2) \leq 27 weeks 6 days gestational age at birth and $>$ 30 days chronologic age at study enrollment; 3) \geq 28 weeks 0 days gestational age at birth and \leq 30 days chronologic age at study enrollment; 4) \geq 28 weeks 0 days gestational age at birth and $>$ 30 days chronologic age at study enrollment. The total sample size across these four cohorts is 32 subjects. Enrollment of an additional 2-3 subjects may be allowed for operational reasons. If the 32

subjects enrolled are not balanced across the 4 groups, we instead will look at the correlation between gestational age at birth. With 32 subjects, the margin of errors of a 95% confidence interval for estimating the correlation given the observed correlation values are given below.

Correlation	0.4	0.5	0.6	0.7
Margin of Error	0.6	0.542	0.47	0.38

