A 95% confidence interval will be constructed to evaluate the mean changes in the log of the viral load between baseline (day 1) and weeks 1, 2, 3, 4, 5, and 6. Area under the curve will be calculated for each subject's CMV viral load measurement utilizing the trapezoidal rule. These AUCs will be calculated over the entire course of drug administration. Spearman's correlations will be given for each AUC estimation and also for the AUC after baseline viral load (VL) adjustment. Analysis of variance will be used to investigate whether grouping AUCs into groups (undetected, 100-1000, 1000-10000 and ≥ 10000) would indicate any PD relationships. In addition, changes in CMV viral load from baseline over time (weeks 1 through 6) will be correlated with PK parameters. These data will provide the framework for all PD analyses, where ganciclovir exposures variables will be correlated with the response variables using linear or maximum effect PD models.

Secondary analyses: To investigate the association of secondary outcomes namely, neutropenia, CMV in urine, viral load and resistance to ganciclovir, with plasma concentration, we will utilize inference methods based on Generalized Estimating Equations (GEE) which models repeated binary data. As in the primary analysis, GEE will enable us to compare groups, investigate changes of outcomes over time, and adjust for any covariates.

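### Viral load is assigned to a GEE meant for repeated binary data, and GEE inference on about 32 infants is planned with no small-sample method

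*Protocol*

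**What the plan says.** The secondary-analyses paragraph of Protocol 11.4 concerns the association of "secondary outcomes namely, neutropenia, CMV in urine, viral load and resistance to ganciclovir, with plasma concentration". For all four outcomes it states that "we will utilize inference methods based on Generalized Estimating Equations (GEE) which models repeated binary data", and adds that "GEE will enable us to compare groups, investigate changes of outcomes over time, and adjust for any covariates". SAP Appendix B has the same text. Neither document gives a viral-load cut-off, a link, a working correlation, a variance estimator, a reference distribution or a small-sample correction.

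On sample size, Protocol 11.2 says "The total sample size across these four cohorts is 32 subjects", with 2-3 more allowed for operational reasons, and on the groups "we would like to compare the means of 4 groups (see below) with sample sizes of approximately 8, 8, 8, and 8".

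On repeats, Protocol 8.2.1.1 says "Whole blood will be collected at each study visit from Period 1 through Period 5"; Periods 6 and 7 depend on weight. Sampling ends when intravenous ganciclovir is permanently stopped (Protocol, section 4). On treatment length, Protocol 2.1 says "anecdotal experience suggests that it generally is in the range of two to four weeks of total antiviral therapy".

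The paragraph just before the GEE sentence, in both documents, treats viral load as quantitative. It plans confidence intervals for mean change in log viral load, a viral-load AUC with Spearman correlations, change from baseline correlated with PK parameters, and linear or maximum-effect models. Protocol 11.4 also names mixed models for outcomes measured repeatedly; SAP Appendix B names them for the AUC12 comparison.

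**The concern.** There are two gaps in one sentence.

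First, three of the four outcomes are naturally yes/no at each visit, but viral load is a PCR quantity that the plan itself logs. Read literally, the sentence puts it in a binary model without saying how it becomes binary. That leaves the scale of a secondary endpoint (Protocol 3.2.2) open in the one analysis labelled secondary.

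Second, the usual GEE standard error is justified when clusters are many. Here the clusters are infants, about 32 in all and about 8 per group. The conventional sandwich estimator is biased downwards in that setting, and a chi-square reference ignores that the variance is itself estimated from few units. Rare events make this worse. At stake are associations of exposure with urine CMV, neutropenia or resistance that appear more certain than the data allow.

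**Working it through.** **The plan's own figure.** None is given for the GEE analyses. The only power calculation is the AUC12 ANOVA: means 20, 20, 30, 35 (mean 26.25), SD of means = √(168.75/4) = 6.495, f = 6.495/10 = 0.65, λ = 32 × f² = 13.5, F with 3 and 28 df. Power is 83.1%, against the stated 83%. It reproduces but does not bear on this point.

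**Inputs from the documents.** 32 infants; 4 groups of 8; up to 7 records per infant.

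**Inputs assumed.** 2-7 records per infant (mean 4.3); skewed (log-normal) infant-level exposure; per-visit event rate 0.05-0.66; latent intraclass correlation (ICC) 0.2-0.8. The 0.66 scenario echoes the two-thirds neutropenia figure in Protocol 2.1, but that figure is cumulative over six weeks, not a per-visit rate.

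**Model.** Logit link, exchangeable working correlation, a time term, plus either one exposure covariate (1 df) or the four-group factor (3 df). There is no true effect.

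**Tests compared.**
- Uncorrected: V = A⁻¹ (Σ DᵢᵀVᵢ⁻¹eᵢeᵢᵀVᵢ⁻¹Dᵢ) A⁻¹; Wald statistic W = bᵀV⁻¹b against chi-square on q df.
- Corrected (Mancl-DeRouen): replace eᵢ by (I − Hᵢ)⁻¹eᵢ with Hᵢ = DᵢA⁻¹DᵢᵀVᵢ⁻¹; W/q against F with q and 32 − p df, where p is the number of coefficients (3 or 5).

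The code gave the same robust and bias-reduced standard errors as a standard package on a test dataset. Each scenario had 1,500 or 3,000 runs. The Monte Carlo standard error at 5% is √(0.05 × 0.95/1500) = 0.6 points or √(0.05 × 0.95/3000) = 0.4 points.

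**Rejection of a true null at nominal 5%, 32 infants**

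| Test | Event rate | ICC | Uncorrected | Corrected | Fits failed |
|---|---|---|---|---|---|
| Exposure | 0.50 | 0.5 | 8.4% | 3.8% | 0% |
| Exposure | 0.30 | 0.5 | 8.3% | 4.3% | 0% |
| Exposure | 0.15 | 0.5 | 8.5% | 4.0% | 0.1% |
| Exposure | 0.30 | 0.2 | 9.4% | 4.7% | 0% |
| Exposure | 0.30 | 0.8 | 7.9% | 4.5% | 0% |
| Exposure | 0.66 | 0.5 | 9.3% | 5.1% | 0% |
| Exposure | 0.05 | 0.5 | 17.0% | 6.0% | 2.7% |
| Group | 0.50 | 0.5 | 11.2% | 4.2% | 0% |
| Group | 0.30 | 0.5 | 11.3% | 3.4% | 0.6% |
| Group | 0.15 | 0.5 | 7.6% | 1.3% | 11.3% |
| Group | 0.30 | 0.2 | 12.1% | 3.7% | 0.1% |
| Group | 0.30 | 0.8 | 11.0% | 2.2% | 2.3% |

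With 200 infants (event rate 0.30, ICC 0.5) the uncorrected rates fall to 5.7% (exposure) and 6.1% (group), so the number of clusters is the cause.

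**Continuous outcome.** The same latent variable, fitted by identity-link GEE in the same runs, gave 11.0-11.3% uncorrected and 5.8-6.6% corrected for exposure, and 13.9-15.6% and 6.5-6.9% for groups. Changing the link does not remove the need for a correction.

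**If viral load were made binary.** With an assumed effect of 0.4 latent SD per SD of exposure (ICC 0.5), the corrected test had 72.5% power on the continuous scale. Dichotomised at 50%, 30% and 15% positive, power was 56.1%, 47.7% and 34.1%, which is 16.4, 24.8 and 38.4 points lower. The gap is slightly flattering to the continuous test, whose null rate was 6.1%.

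**The case against.** A reader might infer that viral-load information will be lost because viral load must be dichotomised. The documents do not support that. No cut-off is stated, GEE accepts a continuous outcome with an identity link, and the preceding paragraph already relates quantitative viral load to PK. The power loss shown above would arise only in this one GEE analysis, and only if viral load were made binary there.

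A reader might also infer that the plan's p-values will be too small. That too goes beyond the text, which names GEE-based inference but not an uncorrected sandwich Wald test. In a further simulation (32 infants, 3-6 visits, about 1,000 runs per scenario, ICC 0.3 or 0.6) the uncorrected Wald test rejected in 7.9-14.9%, while the generalised score test from the same GEE rejected in 3.5-4.8%, falling to 0.5% in the sparsest case. Inflation belongs to one test, although the conventional one.

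The sizes rest on event rates and correlations that the documents do not give. At event rates of 30-50% the exposure test exceeds 5% by only about 3-4 points. The 0.05 level is stated only for the AUC12 F test, so no decision rule hangs on the GEE. Neutropenia and resistance are exploratory endpoints (Protocol 3.2.3).

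All of this stands, and it limits the point. It does not answer it: the sentence still pairs a quantitative outcome with a binary method, and still leaves open a choice that matters with 32 clusters.

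**Conclusion.** The point holds as a conditional one. Both documents list viral load under a method described as binary, and plan GEE inference on about 32 infants without a small-sample method. If the uncorrected sandwich Wald test is used, the false-positive rate is about 7-17% across the simulations instead of 5% (7.6-17.0% in the table). The bias-corrected variance with a t or F reference brings it to about 1-6% (1.3-6.0%). The direction holds in every scenario tried; the size depends on the assumed visits, event rates and correlation.

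It is not established that information is lost, or that the trial's p-values will be wrong. The primary AUC12 analysis and the plan's other quantitative viral-load analyses are unaffected.

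**What to change.** Amend the secondary-analyses paragraph in Protocol 11.4 and SAP Appendix B:

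- **Viral load.** Remove it from the binary GEE. Model log10 viral load as continuous with the mixed model for repeated measures already named in 11.4. An identity-link GEE is an alternative, with the same small-sample correction. State how undetected values are handled, since the plan expects them (its viral-load AUC grouping has an undetected category).
- **Binary outcomes.** Use GEE with a stated working correlation, a Mancl-DeRouen variance and a t or F reference, or the GEE score test.
- **Sparse events.** Where the model cannot be fitted, as may happen for resistance, report descriptively or use a penalised (Firth) or exact method as a fallback. Collapsing resistance to ever/never per infant should not be the default. It drops timing and ignores unequal time on treatment, while the objective in Protocol 3.1 includes duration of therapy.

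The cost is SAP wording and standard software, with no extra blood or infants. Intervals become somewhat wider: in the test dataset the exposure standard error rose from 0.231 to 0.268, a ratio of 1.16. Group tests become conservative when events are sparse (1.3% at event rate 0.15, with 11.3% of fits failing), and the score test can be conservative too.

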12 SOURCE DOCUMENTS AND ACCESS TO SOURCE DATA/DOCUMENTS

The site will maintain appropriate medical and research records for this trial, in compliance with ICH E6, Section 4.9 and regulatory and institutional requirements for the protection of confidentiality of subjects. As part of participating in a DMID-sponsored, DMID-affiliated, or manufacturer-sponsored study, the site will permit authorized representatives of the sponsor(s), DMID, the UAB Central Unit and regulatory agencies to examine (and when required by applicable law, to copy) clinical records for the purposes of quality assurance reviews, audits, and evaluation of the study safety and progress.

Documentation of source data is necessary for the reconstruction, evaluation, and validation of clinical findings, observations, and other activities during a clinical trial. Source data are all information, original records of clinical findings, observations, or other activities in a clinical trial necessary for the reconstruction and evaluation of the trial. Examples of these original documents and data records include, but are not limited to, Source Document Worksheets, hospital records, clinical and office charts, laboratory notes, memoranda, subjects' evaluation checklists, pharmacy dispensing records, recorded data from automated instruments, copies or transcriptions certified after verification as being accurate and complete, microfiches, photographic negatives, microfilm or magnetic media, x-rays, and subject files and records kept at the pharmacy, at the laboratories, and medico-technical departments involved in the clinical trial. Source documentation serves to substantiate the integrity of trial data, confirms observations that are recorded, and confirm the existence of study participants. This standard also serves to ensure data quality by creating audit trails and enabling verification that data are present, complete, and accurate. Sites that are participating in this trial should consult the MOP, and DMID/NIAID Source Document Standards (most current version) for specific instruction and forms.

13 QUALITY CONTROL AND QUALITY ASSURANCE

The study site will implement a quality management plan. The quality management procedures are described herein, as well as in the Manual of Procedures and the study site quality management plan (QMP). Per the QMP, data will be evaluated for compliance with the protocol and accuracy in relation to source documents. The study will be conducted in accordance with procedures identified in the protocol. Items to be reviewed include, but are not limited to: eligibility (including informed consent), AE reporting, study/clinical endpoints, follow-up visits, regulatory documents, missed visits, and review of clinical records. Data that will be reviewed, who is responsible for implementation, and the schedule for internal reviews will be specified or referenced in the quality management plan.

The study monitors will verify that the clinical trial is conducted and data are generated, documented, and reported in compliance with the protocol, ICH E6(R1), and the applicable regulatory requirements. Reports will be submitted to DMID and UAB on monitoring activities. The study site research team will provide direct access to all trial-related sites, source data/documents, and reports for the purpose of monitoring and auditing by the sponsor and their designees.

The UAB Statistical and Data Coordinating Center will implement quality control procedures beginning with the data entry system and generate data quality control checks that will be run on the database within 24 hours of new data entered into the system. Full documentation of these checks will be provided to the UAB Central Unit so that any resulting queries can easily be understood and transmitted to the respective site for resolution within a short period of time. These processes are validated by a second programmer and also tested with faulty test data. All of these procedures and processes are described in detail in the DMID 11-0067 Data Management Plan (DMP) specific for this protocol. The DMP defines and provides instructions regarding the conduct of the data management processes, describing in detail the following: the work to be performed, the responsible individuals/groups, applicable SOPs and Guidelines, and required documentation.

14 ETHICS/PROTECTION OF HUMAN SUBJECTS

14.1 Ethical Standard

The investigator will ensure that this study is conducted in full conformity with the principles set forth in The Belmont Report: Ethical Principles and Guidelines for the Protection of Human Subjects of Research of the US National Commission for the Protection of Human Subjects of Biomedical and Behavioral Research (April 18, 1979) and codified in 45 CFR Part 46 and/or the ICH E6; 62 Federal Regulations 25691 (1997).

14.2 Institutional Review Board

Reviewing IRBs must be registered with the OHRP to conduct FDA-regulated studies. In the United States and in other countries, only institutions holding a current US Federalwide Assurance (FWA) issued by OHRP will be allowed to participate in this study.

This protocol, informed consent documents, relevant supporting information, and all types of volunteer recruitment or advertisement information will be submitted to the Institutional Review Board (IRB) for review and must be approved before the study is initiated. Any amendments to the protocol must also be approved by the IRB prior to implementing changes in the study.

The investigator is responsible for keeping the IRB apprised of the progress of the study and of any changes made to the protocol as deemed appropriate, but in any case at least once per year. The investigator must also keep the IRB informed of any significant AEs.

All IRB approved documents as well as relevant study correspondence should be copied and sent to the UAB Central Unit.

For this study, clinical sites will have the opportunity to participate in a Facilitated Central IRB process supported by the UAB Institutional Review Board and the UAB Central Unit. Participating sites will be provided with detailed instructions on required responsibilities for participating an OHRP compliant Facilitated IRB.

14.3 Informed Consent Process

The process of obtaining informed consent must be documented in the medical records, clinic chart, and/or research chart. The consent form must be signed and dated by the subject's parent(s)/legal guardian(s) before participation in the study. A copy of the signed consent form must be provided to the subject's parent(s)/legal guardian(s). Signed consent forms must remain in each study participants study file and must be available for verification by study monitors at any time.

The investigational nature and research objectives of this trial, the procedure, and its attendant risks and discomforts will be carefully explained to the subject's parent(s)/legal guardian(s). A signed informed consent document will be obtained from each subject's parent(s)/legal guardian(s) prior to entry into this study. At any time during participation in the protocol, if new information becomes available relating to risks, AEs, or toxicities, this information will be provided orally or in writing to all enrolled or prospective subject's parent(s)/legal guardian(s). Documentation will be provided to the IRB and, if necessary, the informed consent will be amended to reflect any relevant information.

An investigator shall seek such consent only under circumstances that provide the subject's parent(s)/legal guardian(s) sufficient opportunity to consider whether or not to participate and that minimize the possibility of coercion or undue influence. The information that is given to the subject's parent(s)/legal guardian(s) shall be in language understandable to the subject's parent(s)/legal guardian(s).

Subject's parent(s)/legal guardian(s) will sign the informed consent document prior to any procedures being done specifically for the study. Subject's parent(s)/legal guardian(s) should have the opportunity to discuss the study with their family, friends or personal physician, or think about it prior to agreeing to participate. Subject's parent(s)/legal guardian(s) may withdraw consent at any time throughout the course of the trial. A copy of the informed consent document will be given to the subject's parent(s)/legal guardian(s) for their records. The rights and welfare of the subjects will be protected by emphasizing to them that the quality of their medical care will not be adversely affected if they decline to participate in this study.

